7.1 Adverse Event Classification

The investigator will evaluate all AEs with respect to seriousness, severity (intensity), and causality (relationship to study therapy or device) according to the following definitions and guidelines:

7.1.1 Anticipated Adverse Events

An anticipated event is one that has been identified in previous studies, published literature, or product labeling to be related to the disease state or therapies. A listing of commonly occurring 'anticipated/expected' events in the population being studied can be found in Appendix A. An unanticipated/unexpected adverse event is any adverse event that has not been reported in previous studies, published literature, product labeling, or which is not anticipated in the population being studied (see appendix A).

7.1.2 Serious Adverse Event

An adverse event that warrants additional action, includes *any* untoward event that:

1. Is fatal
2. Is life-threatening
3. Requires inpatient hospitalization or prolongation of existing hospitalization >48 hours.
Exceptions- therefore not reportable:
 - a. Preplanned (prior to the study) hospital admissions unless the hospitalization is prolonged >48 hours beyond the anticipated length of stay.
 - b. Planned admissions (as part of a study – e.g. admission for drug change or titration for treatment of atrial fibrillation)
 - c. 23 hour hospitalizations OR observation.
 - d. Hospitalization for elective procedure (e.g. cardioversion).
 - e. Emergency room visits that do not result in hospitalization.
 - f. Hospitalization to titrate or optimize medical therapy to treat recurrence of atrial fibrillation.
4. Results in persistent or significant disability or incapacity.
5. Results in a congenital anomaly or birth defect.
6. Important medical events that may not result in death, be life-threatening, or require inpatient hospitalization may be considered an SAE when, based on appropriate medical judgment, they may jeopardize the patient and may require medical or surgical intervention to prevent one of the outcomes listed above.

7.1.3 Adverse Event Intensity or Severity Classification

The intensity or severity of each AE will be classified according to the following guidelines:

1. **Mild:** Any event that results in minimal transient impairment of a body function and does not threaten damage to a body structure, and/or does not require intervention other than monitoring (easily tolerated).
2. **Moderate:** Any event which results in moderate transient impairment of a body function or damage to a body structure, or which requires intervention.
3. **Severe:** Any event which is life threatening, results or could result in significant permanent impairment of a body function or damage to a body structure, requires significant and timely intervention to prevent permanent impairment of a body function or damage to a body structure, or which is intolerable or places the subject at immediate risk of harm.

7.1.4 Causal Relationship to Medical or Ablative Therapy

The International Council of Harmonization (ICH) Guidelines (1995) indicate that “reasonable causal relationship” means that “there are facts [evidence] or arguments to suggest a causal relationship.” The causality assessment must be made by the investigator based on information available at the time that the adverse event eCRF is completed. The initial causality assessment may be revised as new information becomes available.

1. **Definitely related:** there is a reasonable temporal relationship to study therapy or device
 - a. follows a known response pattern (e.g., study drug, treatment or device is known to cause this AE)
 - b. there is no alternative etiology or explanation for the event
2. **Probably related:** there is a reasonable temporal relationship which
 - a. follows a suspected response pattern
 - b. no evidence for a more likely alternative etiology though could be unrelated
3. **Possibly related:** there is a reasonable temporal relationship but
 - a. equivocal evidence that the event is study related as opposed to an alternative etiology
4. **Probably not related:** there is not a reasonable temporal relationship OR
 - a. good evidence for a more likely alternative etiology
5. **Not related:** there is not a temporal relationship OR
 - a. clear and compelling evidence that the event is due to an alternative etiology

7.1.5 Device Related Adverse Events

1. **Device-related:** any adverse event for which a causal relationship between the device and the event is a reasonable possibility. The likelihood that the event is device related will also be sub-classified using the approach in 7.1.4 above. The event will be further classified as whether it is a device failure or malfunction (7.1.5.2) and whether it is unanticipated (7.1.5.3), as described in these sections.
2. **Device Failure or Malfunction:** a device has failed if it is used in accordance with the Instructions for Use, but does not perform or function according to Instructions for Use and negatively impacts the treatment by preventing treatment as intended. Such a failure does not necessarily result in significant adverse outcome.
3. **Unanticipated Adverse Device Effect (UADE):** any serious adverse effect on health or safety or any life-threatening problem or death caused by, or associated with a device, if that effect, problem, or death was not previously identified in nature, severity, or degree of incidence in the investigational plan or application (including a supplementary plan or application) or prior medical literature, or any other unanticipated serious problem

associated with a device that relates to the rights, safety, or welfare of subjects. This event needs to be entered into the eCRF SAE pages within 24 hours of the site's knowledge.

7.2 Adverse Event Reporting

The goal is to have an adverse event reporting process that is (a) clear and simple for site investigators and study coordinators to understand and implement, (b) satisfies all regulatory reporting requirements, (c) eliminates any duplication in data collection and reporting, and (d) has a balanced focus on both the drug and ablation arms of the trial.

All related adverse events, serious and non-serious, that occur between the time of randomization and the last study-related procedure/visit will be followed until resolution, stabilization, or to trial completion. Adverse events for subjects who discontinue study participation at any time during the study should be collected/reported through at least the time of discontinuation. In addition, the required Institutional reporting structure will be followed and/or as described in this protocol.

7.3 Serious Adverse Event Reporting

Regardless of causality, the investigator will record all serious adverse events occurring between randomization and the last study-related procedure/visit or completion of the trial into the electronic database within 24 hours of knowledge of the event. DCRI will report all unanticipated/unexpected study related serious adverse events to Mayo Clinic, NHLBI and the DSMB chair within 2 business days of receipt.

The investigator must update the eCRF SAE when important follow-up information (final diagnosis, outcome, results of specific investigations, etc.) becomes available after submission of the initial entry. Follow-up information should be entered within forty eight (48) hours of knowledge. All reportable events will be followed until resolution, stabilization, or to trial completion, whichever occurs first. In addition, the required Institutional reporting structure will be followed and/or as described in this protocol.

7.4 Expedited Event Reporting

Specified events as listed below that meet **serious** criteria (see section 7.1.2 of the protocol), are **related** (possibly/probably/definitely) to either study drug or the ablation device or procedure, and are **unanticipated/unexpected** if occurring between randomization through completion of follow-up (end of trial) require **expedited** reporting to the DCRI and in turn to the appropriate regulatory agencies.

7.4.1 Expedited events include:

1. Unexpected, SAE related to study drug
2. Unanticipated ablation procedure related events
3. Unanticipated Adverse Device Effect (UADEs)
4. Device failures or malfunctions
5. **Events of Interest (EOI):** Drug or ablation therapy or ablation procedure related events

(index and/or follow-up): The related events that resulted in death, and the following events if they are life-threatening or severe in nature; pro-arrhythmic events, myocardial perforation / tamponade requiring intervention, esophageal atrial fistula, and/or severe pulmonary vein stenosis that were life threatening or classified as severe in nature.

7.5 Adverse Event Documentation

All AEs and SAEs must be documented on the appropriate eCRF. The outcome of each AE and SAEs will be tracked through the major endpoints of the trial, if present. Otherwise these events will be tabulated and addressed descriptively, as gleaned from the eCRF.

Expedited Events must be entered on the appropriate eCRF pages or if the electronic database is unavailable for more than 24 hours, the event would be reported on an *Expedited Event Form* and faxed/mailed to DCRI Safety Surveillance within 24 hours of knowledge of the event. When available, the event must be entered into the electronic data base.

DCRI Safety Surveillance

[contact]

Toll Free: [name]

Email: [contact]

[contact]

Toll Free [contact]

It is understood that complete information about the event may not be known at the time the initial report is submitted. The investigator must assess the relationship of the event to the study device or study therapy and should make every attempt to obtain as much information as possible concerning the event. Additional information pertaining to an expedited event should be submitted to DCRI Safety Surveillance as it becomes available. All reported events will be followed until resolution, stabilization, or until the trial completion whichever occurs first.

7.6 Reporting to Regulatory Authorities

7.6.1 Physician Reporting of Drug or Device Adverse Events

Physician reporting of drug or device-related unexpected/unanticipated serious adverse events (as mandated by regulatory authorities) using MedWatch or Council for International Organizations of Medical Sciences (CIOMS) forms, should continue independently of any CABANA reporting.

It is anticipated that physicians and/or the appropriate healthcare professional will complete this reporting by, 1) MedWatch- submit form 3500 for drug or device via the FDA's MedWatch Adverse Event Reporting program online at www.fda.gov/MedWatch/report.htm, by phone [name], or by returning the postage-paid FDA form 3500 downloaded from www.fda.gov/MedWatch/getforms.htm by mail to MedWatch, [name] or fax [name], 2) CIOMS- using <http://www.cioms.ch/index.htm>, postal address: c/- World Health Organization, [name], [contact] or [contact].

7.6.2 CABANA Reporting of Drug or Device Adverse Events

For CABANA trial purposes, adverse events will be reported through the eCRF submission process designed to facilitate notification to DCRI Safety Surveillance and/or their designee. DCRI Safety Surveillance will review and code all SAEs.

The Safety Surveillance Medical Monitor (a physician trained and experienced in safety reporting) will review Events of Interest, and unexpected/unanticipated SAEs related to ablation

therapy or CABANA approved rate or rhythm control drugs. The decision regarding ultimate classification will be made by **individuals within CABANA Leadership** with expertise in antiarrhythmia and ablation therapies and clinical trial experience.

DCRI Safety Surveillance will notify the NHLBI and Mayo within 1-2 business days of an unexpectedness/unanticipated event determined to be related to the drug, device, and/or therapy. The final report will be submitted to the Regulatory Authorities and all participating investigators per regulations. Investigators are responsible for reporting trial unexpectedness/unanticipated events to their reviewing IRB within 10 working days of first learning of the event.

DCRI Safety Surveillance will notify the NHLBI within 5 business days of all reported Events of Interest (as identified above).

7.6.3 Criteria for Withdrawal of Subjects from Study

No subjects will be removed from the study, and attempts will be made to collect follow-up information for all subjects except those who specifically withdraw consent for release of such information.

8.0 Statistical Considerations

8.1 Sample Size and Power Considerations

In initially planning the CABANA trial, several design factors and research objectives were considered in developing an appropriate sample size for the study. First, the number of patients was determined so there would be a sufficient number of endpoints to provide a high degree of confidence (power $\geq 90\%$) for testing the primary hypothesis. Second, important secondary endpoints were considered. Third, it was considered important for the overall sample to be large enough to permit a prudent examination of treatment effects in selected subgroups of patients where AF ablation might be particularly advantageous, or where the question of a treatment benefit from this invasive procedure is particularly relevant. Important pre-specified subgroups of interest in this study include those defined by age, gender, race, AF type (paroxysmal, persistent, or long-standing persistent), AF duration, heart failure class, presence/absence of underlying structural heart disease, presence/absence of hypertension, and ejection fraction. Finally, the sample size was determined to provide a reasonable level of confidence of detecting clinically important therapeutic effects even if current projections of event rates and treatment differences prove to be optimistic.

As described in Section 2.0, the study was originally designed with total mortality as the primary endpoint. However, in early 2013 a careful assessment of the progress of the trial was undertaken by the study leadership. Completely blinded to any treatment-specific outcome data, the two major issues addressed by the leadership group were (1) a lower than expected aggregated mortality rate, and (2) accrual of patients at a rate much slower than projected. Careful consideration of these issues led to a decision to (a) change the primary endpoint of the trial from total mortality to the key secondary endpoint consisting of the composite of death, disabling stroke, serious bleeding, or cardiac arrest, and (b) reduce the sample size to a number that was consistent with the new primary endpoint. The following paragraphs, which outlined the key considerations in determining the original sample size, are also relevant for the revised sample size.

A combination of data from recent AF trials that reflect patient outcomes when treated with drug therapy (rate control or rhythm control) provide useful information on the range of outcomes that would be expected among the patients enrolled in the drug arm of CABANA. These studies include AFFIRM, RACE, STAF, PIAF and AF CHF. Since the study population in CABANA will be most like patients enrolled in the AFFIRM trial, the most reliable estimates of mortality and other endpoint events applicable to the drug arm of CABANA can be obtained from the AFFIRM data. The five-year mortality in AFFIRM was 23.8% in patients assigned to receive rhythm control drugs and 21.3% in patients assigned to rate control drugs. The crude death rate based on a mean follow-up of 3.5 years was 16.4%. However, the Kaplan-Meier curves in the primary AFFIRM publication reflect mortality rates at 3 years of 13% in the rhythm control arm and 11% in the rate control arm. At 3.5 years, mortality was approximately 16% in the rhythm control arm and 14% in the rate control arm. Based on this information, the mortality rate in the drug-treated arm of CABANA was projected to be approximately 12% after 3 years of follow-up and 15% after 3.5 years of follow-up (3.5 years is the average duration of follow-up originally projected for CABANA). With the original secondary endpoint elevated to become the primary endpoint, the incidence of the new primary endpoint is expected to be higher than the mortality rates.

In addition to the control (drug) arm event rate, a key driver of the sample size is the magnitude of the treatment effect (i.e., the reduction in the primary endpoint expected in the ablation arm). A synthesis of information from multiple published sources [48, 58-61, 67] suggests that the event rate in ablation-treated patients has been relatively low (less than 3% per year), which translates to a projected 3-year event rate of 8-9 % or a 3.5 year rate of 10% or less in the ablation arm of the trial (i.e., a reduction by one-third compared to the drug arm).

Another important factor that must be considered in sample size calculations is the extent to which patients randomized to the drug arm may **cross over** to receive an ablation during the course of their follow-up (if the AF and its symptoms are not adequately controlled by drugs). Although there are strict guidelines regarding changes to a patient's assigned therapy, in certain instances a downstream change may be clinically indicated. All crossovers and reasons for them must be carefully documented. However, crossovers of drug-arm patients to receive ablation will have the impact of reducing the event rate of patients randomized to drug therapy (assuming ablation is effective), and diminishing the magnitude of the treatment effect. Allowance for these crossovers is essential in determining the appropriate sample size. It is possible that up to 25-30% of patients randomized to the drug arm will cross over to ablation at some point during follow-up. Although the length of follow-up in the CABANA Pilot study was only 1 year, the rate of crossover to ablation of patients randomized to drug therapy was only 9.7%.

In addition to drug-arm patients crossing over to ablation, there may also be patients randomized to the ablation arm who require drug therapy. The number of patients randomized to ablation, that following randomization decline the procedure and are treated with drugs, is expected to be small and inconsequential in the sample size calculations. However, there will be patients randomized to ablation that during the course of their follow-up after the ablation are treated with drugs, including in some cases membrane-active antiarrhythmic drugs. For purposes of sample size calculations, these patients are assumed to receive the full benefit of ablation in reducing clinical outcomes, although one might argue that antiarrhythmic drugs, with their possible proarrhythmic effects, might attenuate the clinical benefits of the ablation.

Since the primary treatment comparisons in this study will be based on time-to-event methodology using the log-rank test [102] or equivalently, the Cox proportional hazards model

[103], the approach used for calculating sample size requirements for CABANA was based on the method of Schoenfeld [104] developed for the proportional hazards model.

To provide an adequate number of patients in the trial that will be relatively robust under various assumptions regarding the control-arm event rates and the magnitude of the treatment benefit, 2,000-2,200 patients will be enrolled. With a minimum follow-up of 3 years (amounting to an average follow-up of approximately 5 years), 2,200 patients will provide 90% power for detecting a 30% reduction in the new primary endpoint, and 2,000 patients will provide 88% power, assuming a 3-year event rate in the drug arm of 12% and allowing for a 2% loss to follow-up. Thus, the study will have high power for detecting an important benefit if the control arm event rate is consistent with the rate expected based on previous studies. A sample size in this range will also provide acceptable power (86% with 2200 patients and 82% with 2000 patients) for detecting a 25% reduction with ablation in the primary endpoint if the 3-year drug arm event rate is 15%. Thus we will have good power for detecting a more conservative estimate of the benefit in the composite endpoint if the control arm event rate is higher, but still consistent with previous studies. A 25-30% reduction in primary events will be highly important from a clinical and public health standpoint, given the large population of patients in this country and throughout the world who suffer from AF.

This number of patients (2,000-2,200) will also provide adequate power for detecting a 25% reduction in other important secondary composite endpoints listed in section 2.2 such as the endpoints that involve cardiovascular hospitalization where the incidence is expected to be higher than for the primary endpoint.

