TREATMENT REGIMEN(S)	One-half of the subjects will be randomly allocated to treatment with catheter ablation and one-half will be allocated to drug therapy for either rate control or rhythm control.
DURATION OF STUDY PARTICIPATION	Enrollment will occur over approximately 4 years, and subjects will be followed for an average of approximately 5 years.
NUMBER OF SUBJECTS	2000-2200 with a 1:1 randomization ratio
NUMBER OF SITES	Total number: approximately 180 North American Sites: approximately 120 Non-North American Sites: approximately 60
PRIMARY ENDPOINT	Composite of: 1) total mortality, 2) disabling stroke, 3) serious bleeding, or 4) cardiac arrest.
SECONDARY OUTCOMES	Total mortality, Total mortality or cardiovascular hospitalization, Total mortality or stroke or cardiovascular hospitalization, Cardiovascular death, Cardiovascular death or disabling stroke, Arrhythmic death or cardiac arrest, Heart failure death, Freedom from recurrent AF, Cardiovascular hospitalization, Medical costs and resource use and cost effectiveness, Quality of life, Composite adverse events, LA size, morphology and function.
INTERIM ANALYSES	An interim examination of key safety and endpoint data will be performed at regular intervals during the course of the trial. The primary objective of these analyses will be to evaluate the accumulating data for a high frequency of negative clinical outcomes. The interim monitoring will also involve a review of the control arm event rates, patient recruitment, compliance with the study protocol, status of data collection, and other factors which reflect the overall progress and integrity of the study.

Investigator Statement

I have read the protocol, including all appendices and agree that it contains all necessary details for me and my staff to conduct this study as described. I will personally oversee the conduct of this study as outlined herein and will make a reasonable effort to complete the study within the time designated.

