At sites where the 'CABANA Box' has received appropriate approval, all patients enrolled will receive a single 'CABANA Box' recording system to be used for both patient activated event monitoring (throughout the trial), 24 hour autodetect/autocapture (AD:AC) event monitoring and 96 hour full disclosure Holter monitoring throughout the study. During year one, subjects will be asked to record their heart rhythm each month. After the first year, they will be asked for a 24 hour recording twice a year and a 96 hour recording twice a year. Fingertip recordings as well as AD:AC recordings can be transferred via telephone download from the patient's home to the

CABANA monitoring center. Holter recordings will require downloading of information at the enrolling site for data transfer to the CABANA monitoring center. All recordings will be made available to the enrolling center for use in clinical practice.

Follow up monitoring with an alternative system will be required in centers unable to use the “CABANA Box”.

CT/MR imaging studies will be performed where clinically indicated or otherwise part of routine clinical care on ablation subjects after ablation therapy (between 90 days post ablation and the 6 month follow-up) and as indicated for PV stenosis management throughout the trial. The 150 drug therapy patients that received the CT/MR scan prior to initiating drug therapy, will also undergo one research CT/MR scan after therapy is fully established (between 90 days post drug treatment initiation and the 6 month follow-up). CT/MR data will be electronically transferred to a server at the Mayo Biomedical Imaging Resource, the CABANA Trial Image Analysis Lab. Scans will be anonymized at the site using a software tool provided by the Imaging Center. Each clinical center will also perform standard site radiology evaluation and assessment of the CT/MR images according to the sites’ standard clinical practice.

After completion of the 60 month follow-up, subjects will be asked to extend their participation. If agreed upon, subjects will be asked about their current state of health and any clinical events every 6 months by telephone until the last subject enrolled reaches approximately 36 months follow-up.

Follow-up data will also be obtained at the time of treatment discontinuation, with a crossover in treatment strategy, and at the emergence of any primary or secondary endpoints.

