CABANA is a multi-center randomized clinical trial to assess the safety and efficacy of percutaneous left atrial catheter ablation versus antiarrhythmic drug therapy in subjects who are at least 18 years of age and have new onset or under-treated paroxysmal, persistent, or long-standing persistent atrial fibrillation (AF) and warrant therapy for their arrhythmia. The study population consists of 2,204 subjects enrolled at 126 clinical sites over a period of approximately six years. Subjects were randomized in equal proportions (1:1) to receive either catheter ablation or drug therapy and followed at regular intervals for the duration of the study. The minimum length of follow-up will be slightly less than 2 years, and the median duration of follow-up will be approximately 4 years. At study entry and during the follow-up period, extensive clinical, quality-of-life, and economic data are collected.

3. Objectives

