7.3 Missing Data

Missing data will be handled differently for covariates and endpoints. Data for covariates (see Section 8.1) are expected to be complete or near complete for all patients. Where missing data do occur, using single-imputation methods, continuous variables will be imputed using the median value and categorical variables will be imputed using the mode.

Most primary and secondary endpoints are time-to-event analyses which rely on the ability to calculate the time from randomization (or in some cases time from the end of the 90-day blanking period) to when the event occurred or the date of last contact for censored individuals. Here, missing data may occur when: 1) a visit form or question that indicates if an event occurred (or not) is not completed, and 2) a form or question indicates that an event occurred, but

the event date is missing. The first category prevents the assignment of whether an event occurred or not, while the second category prevents calculation of time to the event. In all analyses, we consider only non-missing data in the determination of whether or not an event occurred (i.e., cases in category 1 will not be considered). Time-to-event for known events when the event date is missing (category 2), will be assigned based on the visit with which the event is recorded. For example, if the event is reported on the month 3 visit, then the time to event would be set to 91.26 days ($365/12 * 3$). If the event is reported on the month 6 visit, then the time to event would be set to 182.52 days ($365/12 * 6$), and so on for all visits up to month 96. If patients do not experience an event, and have an event-free status associated with a visit but no visit date on their last known visit, they will be assigned a censor date in the same manner. For patients with multiple events including a death, any imputed non-death event dates (e.g., cardiovascular (CV) hospitalization) will be forced to occur before the date of death.

If an event or censored status is reported, but both the visit number and event/censored date are missing, then the date of event/censor will be imputed using relevant data and considered on a case-by-case basis.

8. Primary Endpoint Analysis

Primary Endpoint: Time from randomization to the first event among a composite of major clinical outcomes consisting of

- Death (all-cause)
- Disabling stroke
- Serious bleeding
- Cardiac arrest

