$$H_0: S_a(t) = S_d(t), \text{ vs.}$$

$$H_a: S_a(t) \neq S_d(t),$$

where $S_a(t)$ is the event-free survivor function for the ablation arm of the trial, and $S_d(t)$ is the event-free survivor function for the drug arm, both of which are a function of follow-up time t . In other words, we are testing whether the event-free survival experience of the two arms of the trial is the same vs. whether it is different. The above hypothesis will be tested at a 2-sided significance level of 0.049 in the ITT population to account for a single interim analysis (see Section 13).

Because the Cox model will be used for calculating a hazard ratio and confidence interval to summarize the difference in outcome between the two randomized arms, the proportionality assumption in the Cox model (i.e., constant hazard ratio over time) will be checked and tested through adding an interaction term (treatment*log(t)) to the Cox model, and by examining a plot of Schoenfeld residuals.

The hypothesis as expressed above will also be used for the time-to-event analyses of secondary endpoints described below using a 2-sided significance level of 0.05.

8.1 Other Analyses of Primary Endpoint Data (as randomized):

Treatment comparison with covariate adjustment. Using the Cox model, the effect of treatment strategy will be tested, adjusting for the following prospectively defined set of baseline patient characteristics that are expected to have a prognostic relationship with the primary endpoint: age (as a continuous variable), sex, minority status, baseline AF type, years since onset of AF, coronary artery disease, history of congestive heart failure, structural heart disease, hypertension, and CHA₂DS₂-VASc score. These characteristics will serve as a prelude to analyses for examining differential treatment effects. Structural heart disease will be defined as: history of valve disease with either surgical correction or percutaneous intervention, history of

cardiomyopathy, mitral valve regurgitation of moderate or greater severity, or mitral valve stenosis of moderate or greater severity.

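### The protocol's 90% and 86% power assume longer follow-up than the SAP describes, and neither document restates power or expected events for the shorter follow-up.

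*Protocol*

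**What the plan says.** Protocol 8.1 gives power on an explicit condition: "With a minimum follow-up of 3 years (amounting to an average follow-up of approximately 5 years), 2,200 patients will provide 90% power" for a 30% reduction, and 88% with 2,000 patients. The three-year drug-arm rate is taken as 12%, with 2% loss to follow-up. For a 25% reduction at a 15% three-year rate it gives 86% and 82%.

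The rest of the protocol describes the same design. The Synopsis says "Enrollment will occur over approximately 4 years, and subjects will be followed for an average of approximately 5 years". Section 4.4.2 runs extended follow-up "until the last subject enrolled reaches approximately 36 months follow-up".

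The SAP overview, before Section 3, describes something else: "The study population consists of 2,204 subjects enrolled at 126 clinical sites over a period of approximately six years". It continues: "The minimum length of follow-up will be slightly less than 2 years, and the median duration of follow-up will be approximately 4 years". SAP 7.3 provides for visits "and so on for all visits up to month 96", which fits a longest follow-up of nearly 8 years. SAP 7.2 nevertheless still treats 3 years as the follow-up that the protocol specifies.

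SAP Section 8 updates the final test, which is "tested at a 2-sided significance level of 0.049 in the ITT population". The SAP gives neither power nor an expected or target number of primary events.

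**The concern.** Section 8.1 is the only place in either document that quantifies power for the primary endpoint, and the trial described in the SAP does not meet its condition. In a time-to-event trial, power comes from the number of events. With enrollment complete at 2,204, less follow-up means fewer events at the same event rates.

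A reader judging a non-significant primary result would probably carry the 90% and 86% over to this trial. The second figure matters more. It covers the more conservative effect, for which 8.1 claims good power, and it already assumes the higher event rate.

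**Working it through.** **Inputs.** Protocol 8.1: Schoenfeld's method, hazard ratios 0.70 and 0.75, three-year drug-arm rates 12% and 15%, 2% loss. Protocol 4.1: 1:1 allocation. Protocol 8.2: two-sided tests. Protocol 8.2.7: alpha 0.05. SAP overview: N = 2,204, minimum just under 2 years (taken as 1.9), median 4, enrollment over 6 years, so a maximum of about 1.9 + 6 = 7.9 years. SAP Section 8: final alpha 0.049.

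**Formulas.** Drug-arm hazard λ = −ln(1 − p₃)/3; ablation hazard HR·λ (exponential hazards assumed).

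Expected events D = 0.98·(N/2)·[P(λ) + P(HR·λ)], where P(λ) is the average of 1 − exp(−λu) over follow-up times u.

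Power = Φ(√(D/4)·|ln HR| − z), where z is the two-sided critical value.

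**Step 1: reproduce the protocol.** Four years of enrollment plus a 3-year minimum gives follow-up uniform on 3–7 years, mean 5, as stated.

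- 12%, HR 0.70: λ = −ln(0.88)/3 = 0.0426; average event probabilities 0.191 (drug) and 0.138 (ablation). D = 0.98 × 1,100 × 0.329 ≈ 354.6. Power is 91.9%, against 90% stated. With 2,000 patients it is 89.3%, against 88%.
- 15%, HR 0.75: λ = 0.0542; probabilities 0.236 and 0.183; D ≈ 451.4. Power is 86.3%, against 86% stated. With 2,000 patients it is 83.0%, against 82%.

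All four figures come back within 2 points. With N = 2,204 and alpha 0.049 on the same 3–7 years, the results are 355.3 events and 91.8%, and 452.2 events and 86.2%. The alpha change is therefore not the issue.

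**Step 2: events needed at alpha 0.049.** D = 4(z_α/2 + z_power)²/(ln HR)² gives 332 for 90% at HR 0.70 and 449 for 86% at HR 0.75.

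**Step 3: SAP follow-up, N = 2,204, alpha 0.049, range 1.9–7.9 years.**

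| Follow-up shape | Mean (y) | Events / power, HR 0.70, 12% | Events / power, HR 0.75, 15% |
|---|---|---|---|
| Uniform, no withdrawal (median 4.9) | 4.90 | 346.7 / 91.2% | 440.9 / 85.4% |
| Half on 1.9–4, half on 4–7.9 (median 4) | 4.45 | 317.0 / 88.6% | 403.9 / 82.2% |
| Truncated exponential (median 4) | 4.28 | 305.9 / 87.5% | 390.2 / 80.9% |
| Triangular (median 4) | 4.21 | 302.7 / 87.2% | 386.6 / 80.5% |
| Beta, concentration 4 (median 4) | 4.14 | 297.9 / 86.6% | 380.6 / 79.9% |
| Beta, concentration 8 (median 4) | 4.07 | 294.4 / 86.2% | 376.6 / 79.5% |

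The first row shows that the shorter minimum alone costs little. The loss comes from the median of about 4. Against 91.9% and 86.3%, the median-4 rows lose 3.3–5.7 and 4.2–6.9 points.

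**Step 4: if the median is observed follow-up.** Take administrative follow-up uniform on 1.9–7.9 years. The fraction still at risk at 4 years is (3.9/6)·exp(−4r), which equals 0.5 when the total exit rate r is 6.56% a year. Count assumed deaths of 2–3% a year within that rate, treat the rest as withdrawal, and drop the separate 2% loss. The results are 314.9–322.8 events and 88.4–89.2%, and 401.0–411.0 events and 81.9–82.8%.

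**Step 5: what event rate would restore the stated power?** Over the five median-4 shapes, a three-year drug-arm rate of 12.6–13.6% restores 90% at HR 0.70, and 16.8–18.0% restores 86% at HR 0.75.

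**The case against.** The strongest reply is that 8.1 is a conditional planning statement and the SAP openly reports what happened instead. It commits in 7.2 to reporting follow-up percentiles and the numbers reaching 3 and 5 years. The SAP never repeats the 90% or 86%. A finished trial is read from its events, hazard ratio and confidence interval, not from a recalculated design power. This is fair, and it limits the consequence. But the protocol's figures remain the only ones on record, and nothing tells the reader that their condition has lapsed.

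The follow-up shapes are assumed, and the SAP does not say whether its median is potential or observed. Both points stand, which is why the result is a range. Every median-4 reading tried here still falls short of 332 and 449 events.

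Protocol 8.1 already accepted 88% and 82% at 2,000 patients, and the more favourable readings stay at about that level. That is true, but with 2,204 enrolled the figures a reader would use are those for 2,200.

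The event rate could be higher than assumed. Protocol 8.1 says "the incidence of the new primary endpoint is expected to be higher than the mortality rates", and its 12% matches the mortality projection. The HR 0.70 shortfall could well vanish for this reason. The HR 0.75 scenario already uses 15% and would need about 17–18%, and the documents give no projected rate for the composite.

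The method used here returns 91.9% where the protocol states 90%, and 8.1 does not show how crossover enters its figures. The exact protocol calculation is therefore unseen. That favours the like-for-like loss as the main measure. Comparing with the stated 90% would make the loss look smaller, not larger.

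**Conclusion.** The point holds. The power stated in 8.1 rests on follow-up that the SAP's trial does not have, and neither document restates power or expected events. At the protocol's rates, expected events fall from about 355 to 294–317 (HR 0.70) and from about 452 to 377–404 (HR 0.75). Power becomes about 86–89% and 79–82%. If the SAP median is observed follow-up, it is about 88–89% and 82–83%.

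This rests on exponential hazards, assumed follow-up shapes and no separate allowance for crossover, so confidence in the exact size is medium. The effect is modest: HR 0.70 power stays above 85%, and the test, alpha, sample size and estimand are unaffected. It is worth correcting before the result is read.

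**What to change.** Leave Protocol 8.1 as the planning record. Add a short SAP paragraph that:

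- says follow-up is shorter than 8.1 assumed, so the 90% and 86% no longer apply;
- gives the coordinating center's own expected number of primary events and power at two-sided alpha 0.049, computed from the actual pooled follow-up distribution, for HR 0.70 at 12% and HR 0.75 at 15%;
- adds a sensitivity analysis over the event rate;
- states whether the median of about 4 years is potential or observed follow-up.

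The ranges above show only the size of the gap and should not be copied into the SAP. The cost is one calculation on pooled data and one paragraph. The stated power becomes slightly less favourable; no patients, follow-up or analyses are added.
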